## **4.2 Scientific Rationale for Study Design**

### **4.2.1 Rationale for Endpoints**

#### **4.2.1.1 Efficacy Endpoints**

##### **4.2.1.1.1 Primary Efficacy Endpoint**

This study will use RFS based on recurrence as assessed by the investigator as the primary endpoint. RFS is an acceptable measure of clinical benefit for a late stage study that demonstrates superiority of a new antineoplastic therapy, especially if the magnitude of the effect is large and the therapy has an acceptable risk/benefit profile.

Investigator identified recurrence will be used to make treatment decisions as well as for exploratory efficacy analyses where specified.

New incident cases of melanoma will be distinguished from recurrences by a local pathologist. A pathologist will review skin lesion biopsy specimens and resection samples to identify if an intraepidermal component exists in the sample. If an intraepidermal component does exist, it is consistent with a new primary melanoma as opposed to a regional (in-transit) or distant metastatic recurrence. Refer to Appendix 12 for details regarding Guidance for Distinguishing Primary Cutaneous Melanomas from Cutaneous Metastases of Melanoma. New incident cases of melanoma and second cancer diagnoses are not counted as events for recurrence-free survival. A central imaging vendor will be used to collect, clean, and hold tumor imaging.

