- Participant with confirmed disease recurrence radiographically and/or by exam with subsequent biopsy while on Part 1 treatment with pembrolizumab or placebo must stop Part 1 study treatment. Participants on Part 1 treatment with placebo can be screened for Part 2 therapy with pembrolizumab.
- Confirmed disease recurrence identified by investigator (radiographically and/or by exam with subsequent biopsy) or confirmed progression per iRECIST if clinically stable during Part 2 treatment outlined in Section 8.11 (exception if the Sponsor approves treatment continuation).
- Any progression or recurrence of any malignancy, or any occurrence of another malignancy that requires active treatment (hormonal and/or antineoplastic therapy).
  - Exceptions to secondary malignancy include basal cell carcinoma of the skin, squamous cell carcinoma of the skin, new nonulcerated primary melanoma  $<$ 1mm in depth with no nodal involvement, or carcinoma in situ (eg, breast carcinoma, cervical cancer in situ) that have undergone potentially curative therapy. Exceptions should be discussed with the Sponsor prior to continuing therapy or remaining in follow-up.
  - Diagnosis of a new primary melanoma  $>$ 1mm or  $<$ 1mm with ulceration will result in discontinuation of therapy in Part 1 or Part 2 and make participant no longer eligible for Part 2 therapy.
  - Investigator may submit a Sponsor consultation form to request a participant be unblinded if the participant develops a second malignancy including a new primary melanoma  $>$ 1mm or  $<$ 1mm with ulceration.
- Noncompliance with study treatment or procedure requirements.
- Discontinuation of treatment may be considered for participants who have attained a confirmed CR and have been treated for at least 8 cycles (at least 24 weeks), receiving at least 2 doses of pembrolizumab beyond the date when the initial CR was declared.
- Recurrent Grade 2 pneumonitis.
- Completion of 17 cycles during Part 1 therapy.

Note: Participants who complete Part 1 therapy are still eligible for Part 2 therapy if they meet Part 2 eligibility guidelines. For any participant who is not able to complete the

required 17 cycles, a notification to the Sponsor is required to determine if it would impact eligibility for entry into Part 2.

- Completion of 17 cycles or 35 cycles with pembrolizumab as assigned in Part 2.

Note: The number of treatments is calculated starting with the first dose.

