### **8.1.11 Participant Blinding/Unblinding**

STUDY TREATMENT IDENTIFICATION INFORMATION IS TO BE UNMASKED DURING PART 1 ONLY IF NECESSARY FOR THE WELFARE OF THE PARTICIPANT. EVERY EFFORT SHOULD BE MADE NOT TO UNBLIND.

For emergency situations where the investigator or medically qualified designee (consistent with local requirements) needs to identify the drug used by a participant and/or the dosage administered, he/she will contact the emergency unblinding call center by telephone and make a request for emergency unblinding. As requested by the investigator or medically qualified designee the emergency unblinding call center will provide the information to him/her promptly and report unblinding to the Sponsor. Prior to contacting the emergency unblinding call center to request unblinding of a participant's treatment assignment, the investigator who is a qualified physician should make reasonable attempts to enter the toxicity grade of the AEs observed, the relation to study drug, the reason thereof, etc., in the medical chart. If it is not possible to record this assessment in the chart prior to the unblinding, the unblinding should not be delayed.

In the event that unblinding has occurred, the circumstances around the unblinding (eg, date, reason and person performing the unblinding) must be documented promptly, and the Sponsor notified as soon as possible.

Once an emergency unblinding has taken place, the principal investigator, site personnel, and Sponsor personnel (with the exception of the blinded study statisticians) may be unblinded so that the appropriate follow-up medical care can be provided to the participant.

For studies that require non-emergency unblinding as part of the study design (eg, disease progression) to support treatment decisions, instructions in Procedure Manual should be followed. The emergency unblinding center should not be used for this purpose.

Once a non-emergency unblinding has taken place (ie, after first recurrence), the principal investigator, site personnel, and Sponsor personnel (with the exception of the study blinded statisticians) may be unblinded to the participant's data so that the appropriate follow-up medical care can be provided to the participant.

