Participants whose treatment assignment has been unblinded by the investigator/delegate and/or nonstudy treating physician should continue to be monitored. Participants who qualify for Part 2 per the eligibility criteria in Section 6.7 may continue on the study.

The process for nonemergent unblinding at the time of disease recurrence in Part 1 requires the investigator to submit a Sponsor consultation form to the study clinical team requesting authorization for official unblinding upon disease recurrence and consideration to proceed into Part 2 of the study (Crossover/Rechallenge treatment). After unblinding is complete, the site will assess the participant's eligibility for Part 2 of the study and notify the Sponsor prior to beginning Part 2. The entry criteria for Part 2 are detailed in Section 6.7.

During the study, all data should be entered as soon as possible after a protocol visit or procedure is conducted. Upon first recurrence, every effort must be made to have all pending data entered into the eCRFs within 1 business day or before the site is unblinded to the

participant's treatment assignment. The site should ensure data for disease recurrence is entered in the database prior to unblinding. Additionally, any AEs and/or SAEs should be reported and causality attributed in the database prior to unblinding.

The study will be considered unblinded once the RFS endpoint has been achieved and has been reviewed by the eDMC. The Sponsor will identify to the sites the specific unblinding procedures to be followed.

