## **9.2 Responsibility for Analyses/In-house Blinding**

The statistical analysis of the data obtained from this study will be the responsibility of the Clinical Biostatistics Department of the Sponsor.

The Sponsor will generate the randomized allocation schedule(s) for study treatment assignment for this protocol, and the randomization will be implemented in IRT.

Part 1 of this study will be conducted as a double-blind study under in-house blinding procedures. Blinded Sponsor personnel will remain blinded throughout study conduct and the official, final database will not be unblinded until medical/scientific review has been performed, protocol deviations have been identified, and data have been declared final and complete. In addition, the site radiologist(s) will perform the imaging review without knowledge of treatment group assignment and provide their results to the site investigator.

Blinding with respect to planned efficacy interim analyses is described in Section 9.7 – Interim Analyses. Protocol-specified blinding to treatment assignment will be maintained at all investigational sites.

Part 2 of this study is open-label, so individuals participating in Part 2 will not remain blinded throughout the entire conduct of the study.

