### **9.4.1 Efficacy Endpoints**

#### **9.4.1.1 Primary Efficacy Endpoint**

##### **Recurrence-free Survival (RFS)**

Recurrence-free Survival is defined as the time from randomization to any of the following events: recurrence of melanoma at any site (local, in-transit or regional lymph nodes or distant recurrence) or death due to any cause. New incident cases of melanoma and second cancer diagnoses are not counted as events for recurrence-free survival. See Section 9.6.1 – Statistical Methods for Efficacy Analyses for the definition of censoring.

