## **10.12 Appendix 12: Guidance for Distinguishing Primary Cutaneous Melanomas From Cutaneous Metastases of Melanoma**

If the diagnosis is made in the context of an appropriate clinical history, it is usually not difficult to establish a correct pathologic diagnosis of either primary cutaneous melanoma or cutaneous metastasis of melanoma. Occasionally it may be extremely difficult to definitively determine whether a melanoma is a primary tumor, or a metastasis based upon pathological examination alone. This is particularly the case for a melanoma located in the dermis that lacks an in situ component in the overlying epidermis. In many instances, such tumors represent a primary melanoma with regression of the superficial dermal and epidermal components. The pathologist should recognize this phenomenon by the presence of some subtle clues such as:

- the presence of rare single atypical epidermal melanocytes,
- epidermal thinning with loss of rete ridges,
- fibrosis and vascular proliferation in the dermis overlying the lesion,
- defect in the band of superficial solar elastosis,
- band-like lymphohistiocytic inflammatory cell infiltrate which usually includes numerous pigment-laden macrophages.

In cases where difficulty remains, it is prudent to examine microscopically additional tissue from the lesion, including further sections cut from the original and additional tissue blocks.

In some instances, it is impossible to be certain from the pathologic features alone whether a melanoma is primary or metastatic. In such cases, correlation with clinical information is essential, as this may provide further and critical clues (eg, a history of a pigmented plaque that disappeared over time leaving a lump in the dermis would be strong evidence in favor of a primary melanoma with a regressed superficial/epidermal component). Furthermore, some primary melanomas may arise in the dermis without origin from the epidermis, including some cases of desmoplastic melanoma, melanomas arising in congenital nevi and blue nevus-like melanoma. The presence of an associated, benign nevus component is evidence favoring that a lesion is a primary melanoma and not metastatic melanoma.

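### Section 7.1 allows non-emergency unblinding for a second cancer, which is not an RFS event, without first fixing the new-primary versus recurrence call or isolating recurrences judged afterwards

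*Protocol*

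**What the plan says.** Protocol 7.1, in its list of reasons for stopping treatment, gives this route: "Investigator may submit a Sponsor consultation form to request a participant be unblinded if the participant develops a second malignancy". The sentence goes on to include a new primary melanoma that is thicker than 1 mm, or thinner but ulcerated. The same section stops treatment for anyone deliberately unblinded in Part 1 before recurrence, but keeps that person in follow-up.

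On the endpoint, Protocol 4.2.1.1.1 states: "This study will use RFS based on recurrence as assessed by the investigator as the primary endpoint". It also says: "New incident cases of melanoma will be distinguished from recurrences by a local pathologist". Section 9.4.1.1 adds: "New incident cases of melanoma and second cancer diagnoses are not counted as events for recurrence-free survival". The synopsis records that there is no clinical adjudication committee, and Section 8.2.1.2 describes central image review only as a possibility.

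On unblinding, Section 8.1.11 begins its rule on who may learn the arm with: "Once a non-emergency unblinding has taken place (ie, after first recurrence". The investigator and site staff are among those who may then be told. For recurrence, Sections 6.7 and 8.1.11 add a safeguard: "The site should ensure data for disease recurrence is entered in the database prior to unblinding". They also ask for AEs, SAEs and causality to be entered first.

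On analysis, Table 8 of the protocol and Table 1 of the sSAP contain no censoring rule for unblinding. Both documents plan one RFS sensitivity analysis that counts new primary melanomas as events. They plan another that censors events occurring after new anticancer therapy or after two or more consecutive missed assessments.

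**The concern.** The recurrence route is built with care: the event is recorded, then the arm is disclosed, and by then the RFS outcome for that participant is settled. The second-malignancy route has neither feature. The RFS outcome is still open when the arm is disclosed, and no sentence requires the classification that decides whether an RFS event has occurred to be entered first.

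That classification can be a matter of judgement. Appendix 12 concedes: "In some instances, it is impossible to be certain from the pathologic features alone whether a melanoma is primary or metastatic". It asks for correlation with clinical information in such cases, and that information comes from the site.

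Two things are at stake: whether the index lesion keeps its label once the arm is known, and whether later recurrences in that participant are looked for and called in the same way in both arms. Both bear on the primary endpoint, which is assessed locally.

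**Working it through.** **1. The plan's own figure.** Inputs are from Protocol 9.8.1 and 9.9.1: 128 and 179 events, HR 0.60, one-sided alpha 0.025, 1:1 allocation. Method: Lan-DeMets O'Brien-Fleming spending at information fraction 128/179 = 0.715, with drift (√D/2) × |ln HR|.

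- Drift at the interim: (√128/2) × 0.511 = 2.89. Drift at the final analysis: (√179/2) × 0.511 = 3.42.
- Bounds: Z = 2.407 and 2.003, against 2.4115 and 2.0029 in Table 12.
- Power: 0.924, against 0.9190.

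The figures reproduce to within rounding and approximation. This point does not challenge them, and the fix would not change them.

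**2. The two unblinding routes side by side.**

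| | Recurrence (6.7, 8.1.11) | Second malignancy (7.1) |
|---|---|---|
| Is the trigger an RFS event? | Yes | No |
| Sponsor consultation? | Yes | Yes |
| Disease data entered before unblinding? | Required | Not stated |
| RFS still to be judged afterwards? | No | Yes |
| Within the 8.1.11 description of non-emergency unblinding? | Yes | No |

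**3. What the planned sensitivity analyses catch.**

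- Counting new primaries as events: the index lesion is an event under either label, so this analysis is largely unaffected by relabelling. It gives no information on later recurrences judged with the arm known.
- Censoring at new anticancer therapy: this removes later events in participants who started such therapy. It misses those whose second cancer led to none.
- Neither analysis uses the date of unblinding.

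**4. Possible size.** The documents give no rate of second cancers or of unblinding, so a range of 1% to 6% is assumed.

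- Participants unblinded: 954 × 0.01 ≈ 10, to 954 × 0.06 ≈ 57.
- RFS events among them at the trial-wide proportion, 179/954 = 18.8%: 9.54 × 0.188 ≈ 2, to 57.24 × 0.188 ≈ 11.
- These are upper figures for the assumed rates, because only follow-up after the unblinding counts. That holds provided recurrence risk after a second cancer is no higher than in the trial overall.

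**5. What a few one-sided calls would do (scale only).**

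- At HR 0.60, 179 events split as 179/1.6 ≈ 111.9 placebo and 67.1 pembrolizumab. Three extra placebo events give 67.1/114.9 ≈ 0.584.
- With no treatment effect there are about 89.5 events per arm. Three extra placebo events give 89.5/92.5 ≈ 0.968. Three uncounted pembrolizumab events give 86.5/89.5 ≈ 0.966. In the latter case, recomputing the two-look crossing probability with the loss spread in proportion over both looks gives a one-sided error of about 0.041 instead of 0.025.
- Calls in the other direction would move the HR the other way. Nothing in the documents fixes the number of such calls or their direction.

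**The case against.** The strongest reply is that this is a wording gap with protections already around it. Much of that stands.

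- **Unblinding is not automatic.** It needs a request to the Sponsor, and 8.1.11 limits unmasking in Part 1 to the participant's welfare.
- **The trigger presupposes a diagnosis.** A reader might infer that the protocol permits unblinding before the lesion has been classified. It does not say so. A second malignancy must have developed, a local pathologist makes the call, and a new cancer outside the study condition is reportable like an SAE within 24 hours during the collection window. The documents are silent on whether the RFS classification must be entered first, and an SAE report does not fix it.
- **A reader might infer that no planned analysis would show a problem.** That is wrong. The new-primary sensitivity analysis speaks directly to relabelling of the lesion.
- **A reader might infer that the bias must favour pembrolizumab,** because recurrence opens Part 2 for placebo participants. But participants who completed pembrolizumab and recur more than 6 months after the last dose may also enter Part 2 (6.7). Once a qualifying new primary has been diagnosed, Part 2 is closed under 7.1, so that motive does not carry over to later assessments.
- **A reader might see a contradiction with Section 9.2,** which says: "Protocol-specified blinding to treatment assignment will be maintained at all investigational sites". The conflict is slight, since 7.1 is part of what the protocol specifies.
- **Appendix 12 regards the distinction as usually not difficult** given the clinical history, and site radiologists read without knowledge of the arm (9.2).
- **Follow-up regardless of second primaries is deliberate.** The Amendment 4 rationale ties it to intention-to-treat follow-up.

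What remains unanswered is narrower. There is no entry-before-unblinding step on this route, 8.1.11 does not recognise the route, and nothing identifies recurrences judged after it has been used.

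**Conclusion.** The concern holds in this limited form. Section 7.1 opens a pre-recurrence route to unblinding at a site that still has to judge the primary endpoint, and the safeguard written for recurrence is not extended to it. Relabelling of the index lesion is largely covered by a planned analysis; later recurrences judged with the arm known are not isolated by any.

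The size cannot be established from the documents. Under the assumed 1% to 6%, at most about 2 to 11 of 179 events would be judged unblinded, and most of those calls may be unaffected. The three-event examples show scale only and are not predictions; the shift from 0.60 to 0.584 is small beside the final bound of 0.741. The direction is uncertain. The plan's power and boundaries are unaffected. The change is worth making because it is cheap and protects a locally judged primary endpoint, not because bias has been shown.

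**What to change.** Keep the unblinding option, and make these changes:

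1. In Protocol 7.1, require the new-primary versus recurrence classification, the pathology report and AE causality to be in the database before any non-emergency unblinding for a second malignancy, matching what 6.7 and 8.1.11 ask for at recurrence.
2. Reword 8.1.11 so that its description of non-emergency unblinding includes the 7.1 route.
3. Report the number of participants unblinded before first recurrence, by arm, with the number of RFS events recorded afterwards.
4. In sSAP 3.6.1.1, add a supportive RFS sensitivity analysis that censors at unblinding before first recurrence. State that this censoring may be informative, because a second cancer and the decision to unblind may be related to prognosis. It should supplement the intention-to-treat primary analysis, not replace it.

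The cost is a few sentences in each document, a short wait for data entry before a non-emergency unblinding, and one extra model run. Sample size, event targets and boundaries stay as they are.

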## **7.2 Participant Withdrawal From the Study**

A participant must be withdrawn from the study if the participant or participant's legally acceptable representative withdraws consent from the study.

If a participant withdraws from the study, they will no longer receive study treatment or be followed at scheduled protocol visits.

Specific details regarding procedures to be performed at the time of withdrawal from the study, as well as specific details regarding withdrawal from future biomedical research are outlined in Section 8.1.10.1. The procedures to be performed should a participant repeatedly fail to return for scheduled visits and/or if the study site is unable to contact the participant are outlined in Section 7.3.

## **7.3 Lost to Follow-up**

If a participant fails to return to the clinic for a required study visit and/or if the site is unable to contact the participant, the following procedures are to be performed:

- The site must attempt to contact the participant and reschedule the missed visit. If the participant is contacted, the participant should be counseled on the importance of maintaining the protocol-specified visit schedule.
- The investigator or designee must make every effort to regain contact with the participant at each missed visit (eg, telephone calls and/or a certified letter to the participant's last known mailing address or locally equivalent methods). These contact attempts should be documented in the participant's medical record.
- Note: A participant is not considered lost to follow-up until the last scheduled visit for the individual participant. The missing data for the participant will be managed via the prespecified statistical data handling and analysis guidelines.

## **8. Study Assessments and Procedures**

- Study procedures and their timing are summarized in the SoA.
- Adherence to the study design requirements, including those specified in the SoA, is essential and required for study conduct.
- The investigator is responsible for assuring that procedures are conducted by appropriately qualified or trained staff. Delegation of study site personnel responsibilities will be documented in the Investigator Trial File Binder (or equivalent).
- All study-related medical decisions must be made by an investigator who is a qualified physician.
- All screening evaluations must be completed and reviewed to confirm that potential participants meet all eligibility criteria. The investigator will maintain a screening log to record details of all participants screened and to confirm eligibility or record reasons for screening failure, as applicable.
- Procedures conducted as part of the participant's routine clinical management (eg, blood count) and obtained before signing of ICF may be utilized for screening or baseline purposes provided the procedure met the protocol-specified criteria and were performed within the time frame defined in the SoA.
- Additional evaluations/testing may be deemed necessary by the investigator and or the Sponsor for reasons related to participant safety. In some cases, such evaluation/testing may be potentially sensitive in nature (eg, HIV, Hepatitis C, etc.), and thus local regulations may require that additional informed consent, and assent if applicable, be obtained from the participant. In these cases, such evaluations/testing will be performed in accordance with those regulations.

The maximum amount of blood collected from each pediatric participant will not exceed approximately 51 mL per cycle. The amount for adult participants will not exceed approximately 42 mL per cycle.

Repeat or unscheduled samples may be taken for safety reasons or for technical issues with the samples.

